1.2 Clinical Data to Date

There is no available clinical data that pertains to this study in which this protocol developed by Astra-Tech is used to fabricate custom Atlantis abutments prior to guided surgery.

2 Study Objectives

Purpose: To evaluate the possibility of fabricating an ideal CAD/CAM custom abutment that adequately supports the hard and soft tissues in a single edentulous space prior to guided surgery. Evaluation of the custom abutment will be completed at 2 intervals post operatively, with abutment exposure being the primary outcome at follow-up. With knowledge of fabricating the definitive CAD/CAM abutment prior to surgery, soft tissue development can begin immediately and restoration of the implant can be completed without subsequent soft tissue trauma during crown fabrication.

Participants: The study will seek 24 patients with a minimum of 20 teeth who have a bound edentulous space who seek restoration with a dental implant crown.

Procedures (methods): This is a convenience sample, we will recruit subjects who present to the graduate prosthodontics clinic or inquire about the study will be eligible to receive dental implant surgery with subsequent definitive abutment and provisional crown delivery at eight weeks. The group will then be randomly split with half of the group receiving a custom abutment with margin placement .5mm sub-gingivally and half of the group receiving a custom abutment with margin placement 1.5 mm sub-gingivally. Final impression for the definitive e-max all-ceramic crown will be completed at eight weeks with final crown delivery at eleven weeks. Follow-up and data collection will be completed at eight weeks, eleven weeks, and twenty-four weeks post operatively.

Primary Objective

Abutment margin exposure

Secondary Objective

Provisional crown fit.

3 Study Design

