4.1 Inclusion Criteria

1. Partially edentulous with single edentulous space seeking dental implant tooth replacement therapy
2. Age 18-99
3. Edentulous site where previous tooth has been extracted for at least 2 months

4. Minimum of 20 teeth present in mouth
5. Consent to Participate in Clinical Trial
6. Able to tolerate dental implant surgical and restorative procedures

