Final impression for crown fabrication of the abutment will be completed at 8 weeks post surgery using standard clinical protocol. Provisional restorations will be placed onto final abutments delivered at same appointment. These procedures are standard of care for all participants. Research-driven data to include abutment exposure will be collected from subjects regarding fit of the provisional restoration. A peri-apical radiograph of the implant in bone is produced to demonstrate the proper connection of the abutment to the implant at the time of placement of the abutment.

5.6 Visit 6

Appointment 6: Delivery final E-max crown restoration (11 weeks post-op)

Delivery of final crown will be completed using standard clinical protocol at 11 weeks post-surgery. Research driven data to include abutment exposure will be collected from all subjects regarding esthetics of the final abutment.

5.7 Visit 7

Appointment 7: Follow-up 24 weeks post-op

Follow-up of crown restorations will be completed at 6 months post surgery (24 weeks). Research driven data to include abutment exposure will be collected for all subjects. Bleeding on probing measurements will be made to evaluate soft tissue health around the abutments (Standard of Care). A peri-apical radiograph will be made for hard tissue evaluation of the abutment (Standard of Care). Photographs will be taken of restorations per standard protocol (photographs are standard of care). The patient will then be dismissed from the study.

6 Statistical Plan

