6.2 Statistical Methods

Demographics and other baseline characteristics will be presented by means of descriptive statistics.

The primary objective is to compare differences in margin exposure of the abutment between baseline to 6 months later. The null hypothesis is that there is no difference in the margin exposure of the abutment between those 2 visits. Ho will be tested by means of Fisher's exact test, after each abutment margin is classified as it shows or not. A p-value less than 5% will be regarded statistically significant.

Secondary objectives include:

Measurement of the soft tissue response based on the condition of the peri-implant mucosa (bleeding on probing). Fisher's exact test will be used after the site has been evaluated for presence of bleeding or not. Provisional crown fit at delivery of provisional crown- Fisher's exact test will be used after the provisional crown is determined to fit or not.

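### Bleeding on probing is tested as one yes/no per implant: valid but conservative, and a per-subject count of bleeding points would get more from the same probing

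*Combined protocol and SAP*

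**What the plan says.** Section 3.3 makes the condition of the peri-implant mucosa, judged by bleeding on probing, a secondary endpoint. Section 5.7 (Visit 7, 24 weeks) says: "Bleeding on probing measurements will be made to evaluate soft tissue health around the abutments". No other visit lists a bleeding measurement. Section 6.2 then says that Fisher's exact test "will be used after the site has been evaluated for presence of bleeding or not". The significance rule appears in the primary-objective paragraph of 6.2: "A p-value less than 5% will be regarded statistically significant".

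On size and design, section 2 states: "The study will seek 24 patients with a minimum of 20 teeth". It also states: "The group will then be randomly split with half of the group receiving a custom abutment with margin placement .5mm sub-gingivally". The other half receive a margin at 1.5 mm. Inclusion criterion 1 in section 4.1 is "Partially edentulous with single edentulous space seeking dental implant tooth replacement therapy", so each subject contributes one implant. Section 6.1 sets the sample size by feasibility and gives no power, rate or detectable effect.

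The plan does not say how many points around each abutment are probed, how several readings become one yes/no, or which groups are compared on bleeding.

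**The concern.** Probing around an abutment can give several readings, and 5.7 speaks of measurements in the plural. Collapsing them to any bleeding or none scores an implant with one bleeding point the same as an implant that bleeds all round. If most implants have at least one bleeding point, both arms drift towards 100% and the contrast shrinks. With 12 per arm, Fisher's test on a yes/no is also very discrete, so it runs well below its nominal 5%.

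The randomised factor is the depth of the margin under the gum, and bleeding is the only planned measure of mucosal condition. What is at stake is precision on that endpoint. The sample is fixed at 24, so using the graded information is one of the few ways to gain any. Bleeding is listed only at the last visit, so if only a yes/no is recorded there, the detail cannot be recovered later.

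**Working it through.** **The plan's own figure.** The total of 24 cannot be reproduced, because 6.1 gives no rate, effect or power. The check therefore starts from 24 / 2 = 12 per arm.

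**What is compared.** Bleeding is listed only at 24 weeks, so the listed visits allow no before-and-after test. A comparison of the two margin-depth arms is the only evident one, although 6.2 does not name it.

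**Step 1: Fisher on one yes/no per subject, 12 v 12, two-sided 5% (sidedness assumed).** Exact enumeration sums the binomial probabilities of all tables with p < 0.05.
- Size: 0.25% at a true rate of 10%, 1.2% at 20%, 2.3% at 50%, 1.2% at 80%.
- Smallest significant splits: 5/12 v 0/12 and 7/12 v 1/12.
- Power for implant-level rates: 21% (50% v 20%), 61% (70% v 20%), 81% (80% v 20%).
- By the normal approximation, 50% v 20% would need 39 per arm for 80% power, or 45 with continuity correction.

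**Step 2: what collapsing does to the contrast.** Assume k points per implant, point rate m and within-implant correlation r, with a beta-binomial model. Let s = (1 − r)/r. Then P(no bleeding) = product over j = 0 to k − 1 of ((1 − m)s + j)/(s + j).

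With k = 6 and r = 0.3, s = 0.7/0.3 = 2.333. For m = 0.5: 0.5 × 0.65 × 0.731 × 0.781 × 0.816 × 0.841 = 0.127, so 87% of implants have some bleeding. The same formula gives 51% for m = 0.2.

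| Point rates | Point-level gap | Any-bleeding rates | Any-bleeding gap |
|---|---|---|---|
| 25% v 5% | 20 | 60% v 16% | 44 |
| 50% v 20% | 30 | 87% v 51% | 36 |
| 60% v 30% | 30 | 93% v 68% | 25 |

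When bleeding is rare, the yes/no keeps the contrast. When it is common, the yes/no saturates.

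**Step 3: power of the two tests.** Beta-binomial simulation, 12 v 12, with 5,000 runs for Fisher on any bleeding and 1,500 runs (1,000 permutations each) for the permutation test on the per-subject count. Each cell shows Fisher then permutation, in %.

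| Points, correlation | 25% v 5% | 40% v 15% | 50% v 20% | 60% v 30% |
|---|---|---|---|---|
| 4, 0.2 | 45.6, 51.7 | 35.4, 48.7 | 34.6, 60.6 | 18.9, 56.6 |
| 4, 0.3 | 39.6, 45.0 | 35.0, 45.1 | 35.3, 55.2 | 21.3, 50.7 |
| 4, 0.5 | 29.6, 32.0 | 29.0, 35.5 | 32.2, 43.9 | 21.7, 37.5 |
| 4, 0.7 | 20.2, 24.3 | 21.9, 28.2 | 29.0, 37.5 | 22.4, 31.7 |
| 6, 0.2 | 56.2, 61.9 | 36.0, 59.4 | 30.9, 69.5 | 11.6, 65.7 |
| 6, 0.3 | 48.7, 53.8 | 34.8, 52.3 | 33.3, 63.2 | 16.8, 54.3 |
| 6, 0.5 | 35.6, 43.0 | 30.9, 41.5 | 32.6, 47.1 | 20.2, 45.4 |
| 6, 0.7 | 24.5, 26.9 | 24.3, 30.1 | 29.7, 40.3 | 20.7, 35.9 |

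The count is ahead in all 4 × 8 = 32 cells. Smallest and largest gains by column, in percentage points:
- 25% v 5%: 32.0 − 29.6 = 2.4 to 43.0 − 35.6 = 7.4
- 40% v 15%: 30.1 − 24.3 = 5.8 to 59.4 − 36.0 = 23.4
- 50% v 20%: 37.5 − 29.0 = 8.5 to 69.5 − 30.9 = 38.6
- 60% v 30%: 31.7 − 22.4 = 9.3 to 65.7 − 11.6 = 54.1

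The simulation standard error of a permutation figure is at most √(0.25/1,500) = 1.3 points, so differences of a point or two between cells mean little. A repeat simulation kept the sign in all 32.

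**Step 4: type I error.** With equal point rates of 20% or 30% and the same points and correlations, the count test rejects in 2.5% to 4.3% of runs and Fisher on any bleeding in 1.6% to 2.5%.

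**The case against.** The strongest reply is that presence or absence of bleeding is a coherent endpoint, that Fisher's test on it is valid, and that the real limit is 12 per arm. Much of this stands. The count test also stays below 70% power in every cell of the table, so it too would often miss a real difference. The study is a pilot with no power claim, and this is a secondary endpoint. The case report form is not in the documents, so point-level recording may already be in place.

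Two stronger readings are tempting, and the documents support neither.

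- **That the yes/no discards most of the signal.** The loss depends on point rate, number of points and correlation, none of which the plan gives. At 25% v 5% it is only 2 to 7 points. It exceeds half the power only when bleeding is common or weakly clustered, for example 16.8% v 54.3% at 60% v 30%, 6 points, correlation 0.3. Section 4.2 excludes recent smokers and untreated periodontal disease, so low bleeding rates are plausible.
- **That the plan inflates the false-positive rate by counting each probing point as a subject.** Section 6.2 speaks of the site in the singular. Sections 4.1, 4.3.1 and 5.4 use the word for the implant location, and the neighbouring endpoints in 6.2 are one per implant. On that reading there is no inflation.

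Pooling points as if independent would be a mistake: at correlation 0.2 to 0.5 the true error would be about 7% to 18% with 4 points and 13% to 26% with 6. The plan does not propose it, and at zero correlation the error would be 2.5% to 3.6%.

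**Conclusion.** The point holds as one about efficiency, not validity. One yes/no per subject with Fisher's test controls the error rate, conservatively, and leaves unused how many points bleed. Part of the count test's advantage is that it is less discrete and so runs nearer to 5%; the rest is the graded information. It was better in every scenario examined, and the size of the gain runs from negligible in practice to large, depending on how common and how clustered bleeding is. These results rest on 12 per arm with no losses, 4 or 6 points, a beta-binomial model, correlation 0.2 to 0.7 and the four rate pairs shown. Apart from the 12 per arm, these are assumptions and not figures from the documents. The change is worth making because it is cheap and the detail is lost if it is not recorded at Visit 7. No conclusion of the plan is shown to be wrong.

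**What to change.** **Section 5.7:** record bleeding yes/no at each of a fixed number of points around the abutment, the same number for every implant, and state that number.

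**Section 6.2:**
- State that the subject is the unit of analysis and that the comparison is between the two margin-depth arms at 24 weeks.
- Replace Fisher's test on bleeding with an exact permutation test, or an exact Wilcoxon test that allows for ties, on each subject's count of bleeding points. Choose one in advance.
- Report the difference in mean count with a confidence interval.
- Keep the percentage of implants with any bleeding, by arm, as a descriptive result.
- Add one sentence that points on the same implant are not to be pooled as independent observations.

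The cost is a few more boxes on the case report form (if they are not there already), at a probing already planned, and a few lines in 6.2. The downside is slightly more recording and a summary less simple than a yes/no.

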| 9.2 | AUDITING AND INSPECTING..... | 13 |
| 10 | ETHICAL CONSIDERATIONS | 13 |
| 11 | STUDY FINANCES | 13 |
| 11.1 | FUNDING SOURCE | 13 |
| 11.2 | CONFLICT OF INTEREST | 13 |
| 11.3 | SUBJECT STIPENDS OR PAYMENTS | 13 |
| REFERENCES | | 14 |

List of Abbreviations

CAD/CAM – Computer Aided Design/ Computer Aides Milling

CBCT – Cone Beam Computer Tomography

IV –Intravenous

UNC – University of North Carolina

SOD – School of Dentistry

PI – Primary Investigator

CRF – Case Report Form

PHI – Personal Health Information

Study Summary

| | |
|---------------------------------------|--|
| Title | Fabrication of a Definitive CAD/CAM Titanium Abutment Prior to Guided Surgery: A Pilot Study |
| Protocol Number | IRB#13-2376 |
| Methodology | Randomized trial/cohort with 2 arms (experimental) groups |
| Study Duration | 7 months |
| Study Center(s) | Single Center |
| Objectives | To determine if a custom fabricated, patient specific, CAD/CAM titanium abutment that ideally supports the hard and soft tissues with both esthetics and function can be fabricated prior to guided surgery using computed tomography and diagnostic gypsum models |
| Number of Subjects | 24 |
| Diagnosis and Main Inclusion Criteria | Single edentulous space seeking tooth replacement with dental implant |
| Statistical Methodology | Fisher's Exact test |

1 Introduction

This document is a protocol for a human research study. This study is to be conducted according to US and international standards of Good Clinical Practice (FDA Title 21 part 312 and International Conference on Harmonization guidelines), applicable government regulations and Institutional research policies and procedures.

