Using cone beam computed tomography, software is available allowing precise virtual placement of an implant and creation of a milled guide from the plan (D'haese et al. 2010). This milled surgical guide allows the surgeon to place the implant precisely as planned using the patient's CBCT information. Utilizing this virtual plan, it is theoretically possible to fabricate a CAD/CAM patient specific abutment prior to surgery. This allows delivery of the abutment either at surgery or at delivery of the crown following osseointegration. Ultimately, fabrication of the final abutment prior to surgery removes that current necessity of appointing the patient for the final impression. Following surgical implant placement, the next appointment for the patient would be delivery of the final crown. Dental implant therapy could be reduced to 8 weeks of total therapy and 2 total appointments.

While guided surgery for the placement of the implant fixture is extremely precise and is milled from the virtual plan using the patient's CBCT information, surgical guides can have minor error leaving the implant in a position slightly different from the information in the virtual software (Turbush et al. 2012, Sarment et al. 2003). If the abutment and/or crown are produced prior to surgery, these slight differences in the virtual vs. actual position of the implant may provide an abutment and/or crown that either doesn't fit or is esthetically unpleasing.

It is the interest of this study to investigate the possibility of creating a patient specific abutment and provisional crown prior to surgery that is functionally and esthetically pleasing. With this treatment possibility, the time and expense involved with single tooth dental implant therapy will be reduced allowing a better experience for both patient and provider.

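### Section 6.2 plans only Fisher's exact tests and pre-specifies no outcome proportion or confidence interval, although the trial asks whether a pre-surgically made abutment and provisional crown work

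*Combined protocol and SAP*

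**What the plan says.** The aim is stated in three places.

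- The Study Summary gives the objective as "To determine if a custom fabricated, patient specific, CAD/CAM titanium abutment that ideally supports the hard and soft tissues" and goes on to ask whether such an abutment can be made before guided surgery. Section 2 repeats this for the abutment.
- Section 1.1 adds the crown: "It is the interest of this study to investigate the possibility of creating a patient specific abutment and provisional crown prior to surgery". It also warns that small differences between planned and actual implant position "may provide an abutment and/or crown that either doesn't fit or is esthetically unpleasing".
- Section 2 names the primary outcome: "Evaluation of the custom abutment will be completed at 2 intervals post operatively, with abutment exposure being the primary outcome at follow-up". It also sets up the two arms: "The group will then be randomly split with half of the group receiving a custom abutment with margin placement .5mm sub-gingivally", with the other half at 1.5 mm.

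Section 6.2 then gives the analysis.

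- Margin exposure, classified as showing or not, is tested by Fisher's exact test between baseline and 6 months.
- Bleeding on probing, present or absent, gets Fisher's exact test with no comparison named.
- Provisional crown fit, judged once at delivery, gets the sentence "Fisher's exact test will be used after the provisional crown is determined to fit or not", also with no comparison named.
- The only descriptive summary mentioned is for baseline data: "Demographics and other baseline characteristics will be presented by means of descriptive statistics".

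The Study Summary lists Fisher's exact test as the whole statistical methodology. Section 6.1 gives no rate, power or precision target for the 24 subjects. Section 6.3 names an all-randomised population.

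**The concern.** Whether a pre-made part works is a question about a proportion: how often the margin stays covered and how often the crown fits. A Fisher test answers a different question, namely whether two groups or two occasions differ. Both arms receive a pre-surgically made abutment and differ only in margin depth, so no arm in this trial can turn a between-group test into a test of the method.

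At stake is the trial's main statement. Under the plan as written, nothing commits the investigators to report a success rate or its uncertainty. Nor does the plan say how a part that could not be seated or delivered enters the count, or by what criterion a crown is judged to fit. Those choices could then be made with the results in view.

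**Working it through.** **Inputs.** N=24, split in half (section 2), so 12 per arm. Significance is at 5% (section 6.2); sidedness is not stated, so two-sided is assumed. All outcome counts below are illustrations, because the documents give no expected rate. There is no planned figure to reproduce.

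**Step 1: is an estimate planned anywhere?** The Study Summary and sections 2, 3.2, 3.3, 6.1, 6.2 and 6.3 contain no planned outcome proportion, difference in proportions or confidence interval.

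**Step 2: what the primary test can show.** Section 6.2 compares margin exposure between two visits. If the same number of margins show at both visits, that table is the most probable one for its totals, so the Fisher p-value is 1.0 whatever the number. No margins showing at either visit and all margins showing at both give the same result. (Whether Fisher's test suits paired visits is a separate matter and is not needed here.)

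**Step 3: what a crown-fit test could compare.** Fit is judged once, so the between-visit comparison cannot carry over. The natural reading is 0.5 mm v 1.5 mm, but section 6.2 does not mention the arms. Section 5.5 says "Research-driven data to include abutment exposure will be collected from subjects regarding fit of the provisional restoration", so a table of fit against exposure is also conceivable. Neither gives a success rate. The figures in step 4 assume the arm comparison.

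**Step 4: Fisher's test, 12 v 12.** With a and b crowns fitting in the two arms and T=a+b, the probability of a table is C(12,a)·C(12,b)/C(24,T). The two-sided p sums all tables no more probable than the one observed.

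- 12 v 12 (100% fit), 6 v 6 (50%) and 0 v 0 (0%): p=1.0 each.
- T=20, most extreme split 12 v 8: C(12,8)/C(24,20) = 495/10,626 = 0.0466. With its mirror image, p=0.093. By symmetry T=4 (4 v 0) gives the same.
- T=22 (12 v 10) or T=2 (2 v 0): 66/276 = 0.239, doubled p=0.478.
- T=19 (12 v 7, 79.2% fit): 792/42,504 = 0.0186, doubled p=0.037. T=5 (5 v 0, 20.8% fit) gives the same p.

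So p<0.05 is attainable only when 5 to 19 of 24 crowns fit. Outside that range no split between the arms reaches it.

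**Step 5: exact (Clopper-Pearson) 95% intervals.** The lower limit is the 2.5% quantile of Beta(x, n−x+1) and the upper limit is the 97.5% quantile of Beta(x+1, n−x). For x=n the lower limit is 0.025^(1/n); for n=24 this is 0.858.

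| Illustrative result | Proportion | 95% CI |
|---|---|---|
| Crown fits, 24/24 | 100% | 85.8 to 100% |
| Crown fits, 22/24 | 91.7% | 73.0 to 99.0% |
| Crown fits, 12/24 | 50.0% | 29.1 to 70.9% |
| Crown fits, one arm, 12/12 | 100% | 73.5 to 100% |
| Crown fits, one arm, 11/12 | 91.7% | 61.5 to 99.8% |
| Margin shows, 2/24 | 8.3% | 1.0 to 27.0% |
| Margin shows, 6/24 | 25.0% | 9.8 to 46.7% |

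The intervals for 24/24 and 12/24 do not overlap, whereas the Fisher p-value is 1.0 for both when the counts are equal across arms.

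**The case against.** The best reply is that every outcome is classified yes or no before testing, so the counts will exist and anyone can form a proportion from them. This is also a pilot, and no between-group p-value ever tracks an overall rate. All of that is true. What stands against it is that the plan makes no commitment in advance to report a proportion, an interval or a rule for undelivered parts, and these are what the stated aim needs.

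Several stronger readings are tempting and should not be made.

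- A reader might infer that section 6.2 rules out descriptive summaries of outcomes. It does not: the sentence on baseline data contains no restriction, and the plan is simply silent on outcomes.
- A reader might infer that the plan tests crown fit by margin depth. It names no comparison, so every figure in step 4 is conditional on that assumption.
- A reader might infer that the analysis population is left open. Section 6.3 does name all randomised subjects; only the handling of undelivered abutments and crowns is missing.
- A reader might infer that the investigators intend to take a non-significant result as evidence of feasibility. Nothing in the documents says so.

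It is also fair to say that crown fit is secondary, and that only section 1.1 brings the crown into the feasibility aim. The change should therefore lead with margin exposure.

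**Conclusion.** The point holds as a gap between the trial's question and its planned analysis: three binary outcomes, three Fisher tests, two of them without a named comparison, and no pre-specified estimate. That the documents contain no planned estimate rests on their text alone. The size rests on assumptions: 12 per arm, a two-sided test and a between-arm comparison of crown fit. Under these, the test cannot reach significance when 20 or more, or 4 or fewer, of 24 crowns fit, so a method that nearly always works and one that nearly always fails would both read as non-significant. It would be too strong to say that the success rate cannot be known from this trial; it can be calculated, but the plan does not undertake to report it or its uncertainty. This should be changed before analysis.

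**What to change.** In section 6.2, pre-specify these estimates, each overall and by arm with an exact Clopper-Pearson 95% CI, and base feasibility statements on them:

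1. Primary outcome: the proportion of subjects whose abutment margin shows at weeks 8, 11 and 24, the three visits at which sections 5.5 to 5.7 collect it. Use subjects with a delivered abutment, and state the number undelivered beside the estimate.
2. The proportion of provisional crowns that fit at delivery, with the criterion for fit written down beforehand. Start from the section 6.3 all-randomised population with an implant placed, and state how many randomised subjects had none. Count as not fitting a crown that could not be seated because of fit or implant position. List separately, outside the fit count, subjects whose abutment could not be delivered and those who did not reach delivery for unrelated reasons. This keeps abutment failure from being merged into crown fit.
3. The proportion with bleeding on probing at week 24.

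Keep Fisher's test for crown fit as a secondary analysis, naming 0.5 mm v 1.5 mm as the comparison.

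The cost is a few sentences in sections 6.2 and 6.3, a written fit criterion, a recorded reason for any non-delivery and a few more table rows. No visits or subjects are added. The drawback is a visibly wide interval: even 24/24 leaves a lower limit of 85.8%, and 12/12 in one arm leaves 73.5%.
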